### Statistical Analysis

All analyses were conducted using SPSS 25.0^22. Baseline demographic and medical variables for the two conditions were compared using one-way ANOVAs and  $\chi^2$  tests. Intent-to-treat (ITT) analyses were conducted in line with CONSORT guidelines (i.e., all participants who

started the intervention were included) . ITT analyses were completed using maximum likelihood linear mixed model analyses. Between-group differences on primary and secondary outcome variables were also analyzed using linear mixed models. Linear mixed models are considered robust with respect to inclusion of participants with missing data in repeated measures research and are considered superior to traditional repeated measures ANOVA for longitudinal designs . Treatment group (CBT-I or TAU) was specified as the between-subjects factor, and time of measurement was the within-subjects factor. The effect of interest was the treatment group by time interaction coefficient. Models were tested to include a linear and quadratic time coefficient; in final models the quadratic time coefficient was removed for all analyses in which it was not significant. Multiple structures were tested for sigma, and the identity structure was chosen because it provided the best Schwarz's Bayesian Information Criterion (BIC) for each model. The treatment group variable was introduced as a dummy-coded variable with TAU as reference group. An  $\alpha$  of 0.05 was used to determine statistical significance. Effect sizes of 0.20, 0.50, and 0.80 were interpreted as indicating small, medium, and large effects, respectively. Standardized effect sizes for linear mixed models were derived by calculating standard deviation (SD)pooled =  $\sqrt{\frac{((\text{standard error } [se]_1 \cdot \sqrt{n_1})^2 \cdot (n_1 - 1) + (se_2 \cdot \sqrt{n_2})^2 \cdot (n_2 - 1))}{(n_1 + n_2 - 2)}}$  based on existing recommendations .

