Other sleep data outcomes included change in PSQI, DBAS, and sleep diary measures. Most participants provided at least some sleep diary data. On average, participants provided data for 5.6 / 7 days at each assessment. Specifically, sleep diaries were completed by all 24 participants at baseline (mean days of completion = 6.0), by 19 participants at post-treatment (mean days of completion = 5.0), and by 20 participants at the four-week follow-up (mean days of completion = 5.7). All available sleep diary data were included in analyses.

Clinically significant change in ISI scores—the primary outcome variable—was also assessed in two ways. First, a variable indicating whether the ISI changed eight points or more was tested—a change of this magnitude is accepted as a meaningful change in CBT-I trials . Additionally, we calculated and analyzed the proportion of participants in each condition that reached a score below a cut-off of 8 (i.e., 0-7) on the ISI at each time point, indicative of “absence of insomnia” . To compare the proportion of participants who exhibited clinically significant change or reached a score below the cut-off, Fisher’s exact tests were used.

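### The effect-size SD is rebuilt as se × √n from undefined inputs; if se belongs to a fitted mean under linear time, the post-treatment SD is 10–27% too small (random intercept, correlation 0.3–0.7 assumed)

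*Combined protocol and SAP*

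**What the plan says.** The outcomes are analysed with maximum likelihood linear mixed models over three assessments, and "The effect of interest was the treatment group by time interaction coefficient". Time enters as linear and quadratic coefficients, and "in final models the quadratic time coefficient was removed for all analyses in which it was not significant", so a straight line is the default final model. The same section also says that "time of measurement was the within-subjects factor". On covariance it says: "Multiple structures were tested for sigma, and the identity structure was chosen". It does not say whether this refers to a random effect or to the residuals, and it names no random intercept.

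For effect sizes it says: "Standardized effect sizes for linear mixed models were derived by calculating standard deviation", followed by a pooled SD in which each arm contributes (se × √n)², weighted by n − 1. The formula is said to be "based on existing recommendations", with three references. The results are then graded: "Effect sizes of 0.20, 0.50, and 0.80 were interpreted as indicating small, medium, and large effects, respectively". The section does not say which se enters (raw mean, fitted mean or coefficient), at which visit, with which n, or what difference forms the numerator.

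**The concern.** The identity SD = se × √n belongs to a simple mean of n independent observations. A mixed model with linear time does not produce such a mean. Its fitted value at one visit draws on all three visits, so its standard error is smaller than SD/√n. Multiplying by √n then gives a number below the outcome SD, and any difference divided by it looks larger in SD units than it is.

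The formula is offered for mixed models, whose output supplies standard errors of fitted means rather than visit SDs. It also takes one se and one n from each arm, which points to arm means and not to the single interaction coefficient. The fitted-mean reading is therefore the likely one, although the text does not state it. At stake are the standardised effects and their small, medium and large labels, which readers of a pilot may carry into later planning.

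**Working it through.** The documents give no SE, SD, correlation or effect size, so there is no figure of the plan's own to reproduce. The check asks what se × √n returns.

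**Inputs from the documents.** Three visits; 12 participants per arm; post-treatment seven weeks on and follow-up about four weeks later (Participants and Procedures). Time coding is not stated, so I use visit codes 0, 1, 2 and weeks 0, 7, 11.

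**Assumptions.** Separate line per arm, complete data, variance components known, random intercept with within-person correlation ρ of 0.3 to 0.7.

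**Formula.** The variance of the fitted mean at visit time x is (σ²/n) × [ρ + (1 − ρ)h], where h = 1/3 + (x − mean)²/Sxx. Hence (se × √n)/σ = √[ρ + (1 − ρ)h].

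- Codes: mean 1, Sxx = 2. Post-treatment h = 1/3; follow-up h = 1/3 + 1/2 = 0.833.
- Weeks: mean 6, Sxx = 36 + 1 + 25 = 62. Post-treatment h = 1/3 + 1/62 = 0.349; follow-up h = 1/3 + 25/62 = 0.737.

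Example (codes, post-treatment, ρ = 0.3): √(0.3 + 0.7/3) = √0.533 = 0.730.

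| (se × √n)/SD | ρ = 0.3 | ρ = 0.5 | ρ = 0.7 |
|---|---|---|---|
| Post-treatment, codes | 0.730 | 0.816 | 0.894 |
| Post-treatment, weeks | 0.738 | 0.821 | 0.897 |
| Follow-up, codes | 0.940 | 0.957 | 0.975 |
| Follow-up, weeks | 0.903 | 0.932 | 0.960 |

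The SD is therefore 10–27% too small at post-treatment and 3–10% too small at follow-up. For a given numerator, d is multiplied by 1/0.897 = 1.11 to 1/0.730 = 1.37 at post-treatment, and by 1/0.975 = 1.03 to 1/0.903 = 1.11 at follow-up. Weeks 0, 8, 12 give almost the same shortfalls: 10.2–25.8% and 4.4–10.6%.

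**Other readings, post-treatment.**
- No random effect (independent residuals, ρ = 0 in the model): √0.333 = 0.577 or √0.349 = 0.591, so 41–42% too small and a factor of 1.69–1.73.
- Quadratic kept but shared by the arms: factor 1.05–1.14 with a random intercept.
- Raw visit SE with the observed n, or, with complete data, categorical time or a quadratic separate by arm: factor 1.00.
- Maximum likelihood estimation with 12 per arm (4,000-replicate simulation) adds about 3–5 percentage points to the random-intercept shortfall.

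**Effect on labels, numerator held fixed.** A true 0.45 becomes 0.45/0.897 = 0.50 to 0.45/0.730 = 0.62. A true 0.75 becomes 0.75/0.897 = 0.84 to 0.75/0.730 = 1.03.

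**Choice of n.** Diaries came from all 24 at baseline, "by 19 participants at post-treatment", and from 20 at follow-up. Using 24 instead of the providers multiplies the SD by √(24/19) = 1.12 or √(24/20) = 1.10 (even split by arm assumed). This needs no ρ, and it makes the SD larger and d smaller. With diary-like missingness and a fitted SE, the post-treatment shortfall is about 8–24% with n = 12 per arm and 18–33% with the observed 9.5 per arm.

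**Numerator.** Suppose the true arm difference is 0, D, D at the three visits. With codes, a straight line has mean 0.667D and slope D/2, so it fits 0.667D at post-treatment as a visit difference and 0.500D as a change. At ρ = 0.5, d is then 0.667/0.816 = 0.82 or 0.500/0.816 = 0.61 of the truth. If the difference grows linearly, it is 1/0.816 = 1.22. The denominator alone does not settle the direction.

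**The case against.** No error is demonstrated. Every percentage depends on se being a fitted visit-mean SE, which the section never says. The cited sources may define se, n and numerator, and they are not available here. Calling time a factor can be read as categorical, which with complete data would remove the distortion. Post-treatment is also the worst visit. The outputs are descriptive, and the formula alone moves a true 0.80 only to 0.89–1.10, which is still large.

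Most of this stands, and it limits the point to a conditional one. It does not remove it. A plan that grades d against fixed cut-offs should let a reader rebuild d, and this one does not. Values just below a cut-off can cross it. The factor wording sits beside linear and quadratic coefficients, with the quadratic dropped when it is not significant, so linear time remains the default.

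A reader might infer that the trial's effect sizes are inflated. The documents do not support that: the numerator is undefined, and a straight-line numerator can understate the post-treatment difference by more than the small SD overstates it. A reader might also blame this formula for wide swings of label, or for an apparent growth of effect from post-treatment to follow-up. Those would come mainly from the straight-line numerator. The small SD raises post-treatment d more than follow-up d, so it would dampen such growth.

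**Conclusion.** The point holds in conditional form. Without any assumption, the text leaves the se, n, visit and numerator of the effect size unstated, so d cannot be reproduced from the plan.

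On the likely fitted-mean reading with linear time, the denominator is too small by the amounts shown above. The main range rests on a random intercept that the plan does not name, complete data, known variances and an assumed ρ. It is not an upper bound. On the raw-SE reading with the observed n there is no distortion.

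The net direction of bias in the reported d is not established. The interaction estimate, its p-value and the Fisher tests do not use this SD and are unaffected. The consequence is confined to the standardised effects and their labels, but the repair is cheap enough that it should be made.

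**What to change.** Replace se × √n with the pooled within-arm observed SD of the outcome, √{[(n₁ − 1)s₁² + (n₂ − 1)s₂²]/(n₁ + n₂ − 2)}. Here s₁ and s₂ are the SDs of the observed values in each arm at a named visit, and n₁ and n₂ are the numbers observed at that visit. State the numerator of d. Report the unstandardised ISI difference with its 95% CI beside d.

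The planned model and tests stay as they are. If raw visit SEs and the observed n were used, the SD does not change. If fitted SEs were used, this corrects the denominator.

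The cost is a few lines of text and a short recalculation from data already held. Some effect sizes may become smaller.

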## Supplement Table 1. Structure of Cognitive-Behavioural Therapy for Insomnia (CBT-I)

### Session 1: Introduction

1. Psychoeducation about insomnia and the CBT-I treatment including basic principles for coping with sleep problems
2. Setting realistic sleep goals for treatment
3. Discuss the importance of self-monitoring
4. Practice using the Daily Sleep Diary

### Session 2: Relaxation Training

1. Discuss the relationship between relaxation and sleep
2. Review common relaxation practices
3. Practice relaxation exercises in session

### Session 3: Stimulus, Sleep Consolidation and Medication Use

1. Psychoeducation about stimulus control
2. Review progress using sleep consolidation procedures and help adjust the sleep window
3. Learn stimulus control procedures as a means of re-establishing a positive association between bed and sleeping
4. Talk about steps to take control of sleep problems
5. Review common sleep medications, uses and side effects

### Session 4: Cognitive Therapy

1. Discuss the relationship between thoughts, feelings, and sleep behaviours.
2. Review biased ways of thinking about sleep, signs that self-talk may be negative and self-defeating and the categories of negative self-talk
3. Examine attitudes and beliefs about sleep
4. Identify and challenge participants' negative self-talk about their sleep
5. Discuss how worry may interfere with sleep and planning specific worry time

### Session 5: Sleep Hygiene

1. Review the definition of sleep hygiene
2. Discuss how diet/liquids, environment, exercise temperature and sleep-wake schedule can contribute to sleep

### Session 6: Mindfulness and Relapse Prevention

1. Discuss mindfulness techniques as a way to improve insomnia
2. Review common mindfulness practices in session
3. Practice mindfulness exercises in session
4. Emphasize the importance of maintaining treatment gains and continuing to work towards better sleep
5. Discuss effective ways to cope with relapse

